11.2 Analysis of Endpoints

11.2.1 Analysis of Primary Endpoints

With 12 patients enrolled in cohort A, an exact binomial (Clopper-Pearson) 95% confidence interval for the overall response rate can be constructed to have a width of approximately 57.6% (25.0%, 82.5%). This calculation assumes that the overall response rate will approach 55% in cohort A.

Similarly, with 12 patients enrolled in cohort B, an exact binomial (Clopper-Pearson) 95% confidence interval for the overall response rate can be constructed to have a width of approximately 56.9% (14.1%, 70.9%). This calculation assumes that the overall response rate will

approach 40% in cohort B.

11.2.2 Analysis of Secondary and Exploratory Endpoints

Analysis of outcomes will remain descriptive. With 12 patients enrolled in Cohort A, an exact binomial (Clopper-Pearson) 95% confidence interval for the CR rate can be constructed to have a width of approximately 46.3% (2.1%, 48.4%). This calculation assumes that the CR rate will approach 16.7% in cohort A. Similarly with 12 patients enrolled in cohort B, and exact binomial (Clopper-Pearson) 95% confidence interval for the CR rate can be constructed to have a width of approximately 38.5% (0.2%, 38.5%). This calculation assumes the CR rate will approach 8% in cohort B. Assuming adequate follow-up time, Kaplan-Meier survival analysis will be used to assess DoR, PFS, and OS, in the entire cohort. All p-values will be two-sided with statistical significance evaluated at the 0.05 alpha level. Ninety-five percent confidence intervals for median DoR/PFS/OS-time and DoR/PFS/OS proportions, will be calculated to assess the precision of the obtained estimates. Safety will be collected and adverse events will be tabulated per incidence of specific AE terms will be reported for the entire cohort. All analyses will be performed in SAS Version 9.4 (SAS Institute, Inc., Cary, NC) and Stata Version 15.0 (StataCorp, College Station, TX).

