Given this is a pilot study with low subject enrollment with lack of power, analysis of outcomes will remain descriptive. Assuming adequate follow-up time, Kaplan-Meier survival analysis will be used to assess, progression-free survival (PFS), and overall survival (OS), in the entire cohort. All p-values will be two-sided with statistical significance evaluated at the 0.05 alpha level. Ninety-five percent confidence intervals for 1) the overall response rate, 2) median PFS/OS-time, and 3) PFS/OS proportions, will be calculated to assess the precision of the obtained estimates. All analyses will be performed in SAS Version 9.4 (SAS Institute, Inc., Cary, NC) and Stata Version 15.0 (StataCorp, College Station, TX).

Table of Contents

1. STUDY OBJECTIVES.....	8
1.1. Primary Objectives	8
1.2. Secondary Objectives	8
1.3 Exploratory Objectives.....	8
2. BACKGROUND	8
2.1 Disease.....	8
2.2 Rationale.....	9
2.3 Investigational Agents - Umbralisib.....	10
2.3.1 Umbralisib	10
2.3.2 Umbralisib Non-Clinical Studies	10
2.3.3 Non-Clinical Pharmacokinetics.....	11
2.3.4 Non-Clinical Toxicity.....	11
2.3.5 Umbralisib Clinical Pharmacokinetics/Pharmacodynamics	12
2.3.6 Umbralisib Clinical Studies.....	12
2.4 Investigational Agents – Ublituximab.....	13
2.4.1 Ublituximab	13
2.4.2 Ublituximab Non-Clinical Studies	13
2.4.3 Ublituximab Non-Clinical Pharmacokinetics	14
2.4.4 Ublituximab Clinical Pharmacokinetics/Pharmacodynamics	14
2.4.5 Ublituximab Clinical Studies Safety/Efficacy	15
2.5 Risk/Benefit Assessment.....	16
3. SUBJECT SELECTION	17
3.1 Study Population	17
3.2 Inclusion Criteria.....	17
3.3 Exclusion Criteria.....	18
4. REGISTRATION PROCEDURES.....	20
4.1 Patient Registration.....	20
5. STUDY PROCEDURES	20
5.1 Schedule of Evaluations	20
5.1.1 Screening Visit	24
5.1.2 Treatment Phase	24
5.2. Treatment Administration	27
5.2.1 Ublituximab	28
5.2.2 Management of Infusion Related Reactions	29
5.2.3 Umbralisib	30
5.3 General Concomitant Medication and Supportive Care Guidelines	31
5.4 Duration of Therapy and Criteria for Removal from Study	31
5.4.1 Procedures for Subject Removal if Less Than PR at Completion of Combination Therapy.....	32
5.5 Duration of Follow Up	32

6. DOSING DELAYS/DOSE MODIFICATIONS	33
6.1 Ublituximab	33
6.2 Umbralisib	33
7. PHARMACEUTICAL INFORMATION.....	38
7.1 Investigational Agent – Ublituximab	38
7.2 Investigational Agent – Umbralisib	39
7.3 Availability	39
7.4 Investigational Agent Ordering	39
7.5 Investigational Agent Accountability	40

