1.2. Secondary Objectives

Secondary Objectives: Secondary objectives to be evaluated in the study will be complete remission rate, duration of response, and safety.

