11.1 Study Design/Endpoints

In this single center Phase II study we will evaluate the efficacy and safety of umbralisib and ublituximab (U2) as salvage in patients with CLL who have progressed either on a BTK inhibitor or BCL-2 inhibitor. The study will enroll in two parallel cohorts and subjects will be assigned to cohorts based on the previous novel agent containing regimen regardless of how the novel agents were sequenced, **Cohort A** will consist of patients who progress on BTKi containing regimens and **Cohort B** will consist of patients who progress on BCL-2 containing regimens. Subjects who progress on a regimen containing both a BTKi and a BCL-2 inhibitor, will be enrolled in cohort B. Each cohort will be evaluated independently of each other.

Currently available retrospective evidence demonstrates an ORR of ~35-40% when idelalisib is used as first salvage after ibrutinib failure [11]. Given umbralisib's unique molecular properties and combination therapy with ublituximab, we hypothesize a response rate of 55% using U2 as first salvage. Salvage rates with novel agents after venetoclax failure in subjects considered double refractory are unknown. We anticipate close to 90% of patients enrolled in cohort B will have double refractory disease and represent a high risk group. Given these limitations, we anticipate a response rate of 40% in this group based off the efficacy seen with idelalisib after ibrutinib failure.

Because this is a pilot study, no formal sample size/power calculation is required. Given the anticipated different patient populations in each cohort, no cross cohort comparisons will be performed.

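### Kaplan-Meier estimates of DoR, PFS and OS appear to pool the two cohorts, although the plan says each cohort is evaluated independently

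*Combined protocol and SAP*

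**What the plan says.** Section 11.1, and in the same words the Methodology part of the Protocol Summary, sets up two parallel cohorts and states: "Each cohort will be evaluated independently of each other". No endpoint is exempted. Section 11.1 also explains why the cohorts are unlike: "We anticipate close to 90% of patients enrolled in cohort B will have double refractory disease and represent a high risk group". The sentence beginning "Given the anticipated different patient populations in each cohort" goes on to rule out comparisons between cohorts.

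The response endpoints follow this structure. Section 11.2.1 opens "With 12 patients enrolled in cohort A, an exact binomial (Clopper-Pearson) 95% confidence interval for the overall response rate" and then gives the corresponding interval for Cohort B. Section 11.2.2 does the same for the CR rate.

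For the time-to-event endpoints, section 11.2.2 switches to "Kaplan-Meier survival analysis will be used to assess DoR, PFS, and OS, in the entire cohort" and adds: "Ninety-five percent confidence intervals for median DoR/PFS/OS-time and DoR/PFS/OS proportions, will be calculated". The Statistical Analysis Plan part of the Protocol Summary has the parallel sentence without DoR: "Kaplan-Meier survival analysis will be used to assess, progression-free survival (PFS), and overall survival (OS), in the entire cohort". Section 1.2 makes DoR a secondary endpoint ("Secondary objectives to be evaluated in the study will be complete remission rate, duration of response, and safety"); section 1.3 makes PFS and OS exploratory.

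**The concern.** The only explicit instruction for DoR, PFS and OS names a single, undefined *entire cohort*. An analyst who follows it would most likely produce one curve per endpoint for all 24 patients (responders only, for DoR). That does not fit a plan that evaluates its cohorts independently and expects one of them to be a high-risk group.

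If the time-to-event distributions differ, a pooled median falls between the two cohort medians and estimates neither. For DoR the mixture also depends on how many responders each cohort contributes, so the pooled figure moves with the response rates as well as with the durations. If the question is left until data are available, the choice between pooled and separate curves could be made with the results in view.

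**Working it through.** **1. Which reading the text supports.** Three features bear on the meaning of *entire cohort*:

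- The noun is singular and carries no letter, while the same paragraph writes Cohort A and Cohort B when it means one of them.
- The same phrase recurs in that paragraph for adverse-event tabulation, where all treated patients is the obvious sense.
- No by-cohort Kaplan-Meier analysis is specified anywhere.

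Pooled is therefore the natural reading, but not a certain one: the phrase could mean each cohort in full.

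**2. The plan's own figures.** No precision figure is given for any Kaplan-Meier estimate. The by-cohort ORR intervals in 11.2.1 reproduce with Clopper-Pearson limits at n = 12 and x = 12p:

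- Cohort A, x = 12 × 0.55 = 6.6: 25.0% to 82.5%, width 57.6 points.
- Cohort B, x = 12 × 0.40 = 4.8: 14.1% to 70.9%, width 56.9 points.

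The plan thus already accepts n = 12 precision, by cohort, for its primary endpoint.

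**3. What pooling could do to a median.** *Assumption, not from the documents:* exponential times with cohort medians mA and mB. With weight w on Cohort A, the pooled median t solves

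w·2^(−t/mA) + (1 − w)·2^(−t/mB) = 0.5.

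For PFS and OS, w = 12/24 = 0.50:

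| Longer ÷ shorter median | Pooled ÷ longer | Pooled ÷ shorter |
|---|---|---|
| 1.0 | 1.000 | 1.000 |
| 1.25 | 0.893 (11% below) | 1.116 (12% above) |
| 1.5 | 0.811 (19% below) | 1.217 (22% above) |
| 2.0 | 0.694 (31% below) | 1.388 (39% above) |

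Either cohort could be the longer one.

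For DoR the weights are responders. At the plan's assumed ORRs, w = 6.6/(6.6 + 4.8) = 6.6/11.4 = 0.579. At a ratio of 1.5:

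- A longer: pooled median is 0.838 of A (16% below) and 1.257 of B (26% above).
- B longer: pooled median is 1.179 of A (18% above) and 0.786 of B (21% below).

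**4. What separating the cohorts costs in precision.** For a 50% proportion without censoring, the exact 95% interval is:

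- n = 12 (6/12): 21.1% to 78.9%, width 57.8 points.
- n = 24 (12/24): 29.1% to 70.9%, width 41.8 points.

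The by-cohort width is close to the 57.6 and 56.9 points in step 2.

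DoR is harder. The widest distribution-free interval for a median, minimum to maximum, has coverage 1 − 2 × 0.5^n even if every responder progresses: 93.75% at n = 5 and 96.9% at n = 6. With five or fewer responders, 95% limits cannot be reached this way. The chance of that, at the plan's ORRs, is:

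- Cohort A: P(Bin(12, 0.55) ≤ 5) = 0.261.
- Cohort B: P(Bin(12, 0.40) ≤ 5) = 0.665.
- At least one cohort: 1 − (1 − 0.261)(1 − 0.665) = 0.752.
- Both cohorts together giving five or fewer: 0.006.

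**The case against.** The best opposing case is that there is no contradiction. Sections 11.2.1 and 11.2.2 can be read as one consistent pattern: response endpoints by cohort, and everything else, including adverse events, in all patients. A specific analysis sentence normally governs over a general design sentence. The express prohibition in 11.1 is on comparing cohorts, and pooling compares nothing. The primary objective is also written for patients progressing on either drug class. Finally, cohort is fixed by prior treatment, so by-cohort curves can be produced at reporting from the same data, and pooled DoR is better supported given the small number of responders expected.

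Much of this stands. Pooling does not breach the no-comparison rule, and if the independence rule was meant only for response, pooling is allowed. The plan does not say so, however: the rule appears twice without restriction. The sparse-DoR argument is a sound reason to keep a pooled estimate available, but not to leave it as the only one specified. That the curves can be split later is true, but it leaves the headline population to be chosen after the data are seen.

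**Conclusion.** The concern holds, as a minor to moderate point. On its natural reading, the Kaplan-Meier sentence in 11.2.2 and its counterpart in the Protocol Summary do not fit the unrestricted independence rule, and the plan does not reconcile them. This rests on reading *entire cohort* as A plus B, which is likely but not conclusive, and on taking the independence rule as study-wide.

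The size cannot be determined from the documents, which give no time-to-event medians. It is zero if the cohorts share the same distribution. For PFS and OS, under the exponential illustration, it is 11% to 39% of a cohort median for ratios of 1.25 to 2.0. The primary ORR analysis and the sample size are untouched, and the affected endpoints are secondary or exploratory and descriptive.

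**What to change.** Amend section 11.2.2 and the Statistical Analysis Plan part of the Protocol Summary (adding DoR in the latter) along these lines:

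> Kaplan-Meier estimates of DoR (responders), PFS and OS will be produced separately for Cohort A and Cohort B, with 95% CIs where estimable; a pooled estimate may also be reported, labelled as pooled.

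If the sponsor does intend pooling as the main analysis, the plan should define *entire cohort* and state that the independence rule covers response endpoints only.

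The cost is a wording change and one extra by-cohort run on data already collected, with no added patients or visits. Intervals widen as shown, and by-cohort confidence limits for median DoR may well be unavailable in at least one cohort. The words *where estimable* and the retained pooled estimate allow for that.

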11.3 Interim Analysis

As this is a single center pilot study with low enrollment numbers no interim analysis will be performed.

11.4 Reporting and Exclusions

11.4.1 Evaluation of Toxicity

All patients will be evaluable for toxicity from the time of their first treatment with ublituximab or umbralisib. If a subject comes off study due to an adverse event, the subject will be followed for 30 days or until resolution of the toxicity to baseline grade, whichever is longer.

11.4.2 Evaluation of Response

All subjects included in the study will be assessed for response to treatment if they have completed at least one cycle of ublituximab and umbralisib combination therapy.

12. Adverse Event Reporting Requirements

Adverse event (AE) monitoring and reporting is a routine part of every clinical trial. The investigator will be required to provide appropriate information concerning any findings that suggest significant hazards, contraindications, side effects, or precautions pertinent to the safe use of the drug or device under investigation. Safety will be monitored by evaluation of adverse events reported by patients or observed by investigators or research staff, as well as by other investigations such as clinical laboratory tests, radiographic imaging, and physical exam.

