Subjects that meet eligibility criteria will be enrolled and initiate therapy with umbralisib monotherapy for a one cycle lead in Cycle -1. During this lead in cycle of 28 days subjects will initiate umbralisib monotherapy at 800mg orally daily. Starting at C1D1 subjects will initiate combination therapy with U2, on 28 day cycles. During combination therapy, starting cycle 1 subjects will be treated with umbralisib 800mg orally daily and continue daily dosing through all subsequent cycles. Ublituximab will be co-administered on days 1 and 2 (split over days 1 and 2), 8, 15 of Cycle 1 then on D1 for subsequent cycles 2-6. After cycle 6, combination therapy will be completed and subjects will continue with monotherapy umbralisib daily. Subjects will be eligible for response assessment if they complete two cycles of therapy or are noted to have documented clinical progression of disease prior to first study mandated radiographic assessments. Radiographic evaluation for response will occur prior to C3, then occur prior to C7D1 and then every 6 months for up 2 years. Subjects who remain on study after two years will be radiographically evaluated annually thereafter until complete remission or upon evidence of clinical progression. Subjects that have achieved a CR will be followed clinically with physical exam and labwork but will not be required to undergo routine scanning. Study visits will occur monthly on D1 for Cycles 1-7 then every 3 months thereafter as long as patient continues to have clinical benefit.

Subject Selection:

Inclusion Criteria:

A subject will be eligible for participation in the study if he/she meets the following criteria:

1. Subject must have confirmed diagnosis of CLL/SLL and a treatment indication based upon 2018 International Workshop on CLL (IWCLL) criteria.
2. Subject must have documented disease progression on a BTK and or BCL-2 containing regimen as the most recent prior line of therapy. Subjects who were treated with a regimen containing both classes of novel agents will be allowed to enroll and will be enrolled into Cohort B. Subjects who receive a temporizing non-experimental treatment such as monotherapy with an anti-CD20 monoclonal antibody or corticosteroids including high dose methylprednisolone for up to 2 cycles immediately after progression on a BTK or BCL-2 inhibitor will be considered for enrollment after discussion with the study sponsor.
3. Subject must be ≥ 18 years of age.

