5.2.2 Management of Infusion Related Reactions

Since infusion-related hypotension may occur, antihypertensive medications should be held 12-24 hours prior to and throughout ublituximab infusion. Infusion related reactions including severe reactions have been reported with ublituximab administration in patients with CLL. Guidelines are provided below for patients who experience such reactions. Symptomatic infusion reactions, despite premedication, may be treated at the discretion of the treating physician, including but not limited to: oral acetaminophen 650 mg (or equivalent), corticosteroids, antihistamines, oxygen, and bronchodilators.

If an infusion related reaction is observed at any time during the ublituximab treatment, the treating investigator may reduce the infusion flow rate at their discretion.

The following are recommended infusion rate reduction/delay guidelines for patients who experience severe Infusion Related Reactions (IRR's) in which treatment should be interrupted. Final decision for infusion rate reduction/delay or discontinuation resides with the treating investigator.

1st or 2nd Infusion Interruption:

- Hold infusion and closely monitor patient, institute symptomatic medical management until resolution of IRR symptoms. Treating investigator must be notified by research team and documentation should occur in the patient chart.
 - Symptomatic medical management should include administration of acetaminophen, antihistamines, and/or corticosteroids for fever (temperature $>38^{\circ}\text{C}$) and/or chills
 - Physician may order meperidine for persistent rigors, caution to be exercised if

- patient is hypotensive and meperidine may contribute to ongoing hypotension.
- Administer antihistamines and/or corticosteroids for flushing, urticarial, pruritus, or angioedema
- Administer IV fluid boluses for hypotension
- Administer epinephrine, corticosteroids and antihistamines in the event of an anaphylactic reaction
- Following the judgment of the Investigator, and provided the patient is stable, the infusion may be resumed at half the previous rate.
- If the patient does not experience any further IRR symptoms, infusion rate escalation may resume at the increments and intervals as appropriate at the treatment cycle dose (see Section 5.2.1)
- For any Grade 4 infusion related reaction, ublituximab should be stopped indefinitely. Subjects that experience a Grade 4 infusion reaction will not be allowed to be rechallenged.

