5.5 Duration of Follow Up

The anticipated duration of patients on study therapy will be 2 years though patients deriving benefit will be allowed to continue on study beyond two years. Patients removed from study for unacceptable adverse events will be followed until resolution or stabilization of the adverse event even if that period is longer than 30 days after removal.

After withdrawal from protocol treatment, all patients should be followed for AEs for 30 calendar days after their last dose of either study drug. All new AEs occurring during this period

must be recorded and followed until resolution, unless, in the opinion of the investigator, these values are not likely to improve because of the underlying disease.

Subjects who discontinue study treatment for reasons other than disease progression or withdrawal of consent will be followed for progression free survival and survival every 3 months until documentation of disease progression, death or initiation of CLL directed non study treatment.

Visits for subjects with early treatment discontinuation other than disease progression, death or withdrawal of consent, will continue for 3 months after study drug discontinuation. Subjects and study team should collect the following data during this follow-up period:

- ECOG
- Medical history
- Physical exam
- Vital Signs
- Weight
- CBC with differential
- CMP
- CT neck, chest, abdomen and pelvis with contrast every 12 months or as clinically warranted to document disease progression

Subjects who discontinue therapy for any reason except withdrawal of consent will be followed for overall survival for up to 5 years. Survival follow-up will be documented by either chart review if the subject remains an active patient in the investigators clinic or by phone call every 6 months up to 5 years. If subject is not in active follow-up then a chart note should be placed within the patient chart to confirm survival status.

When the first subject enters year five of treatment or follow-up the study may be amended to address continuation of study therapy or follow-up beyond year 5.

6. Dosing Delays/Dose Modifications

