6.2 Umbralisib

Dose delays and modifications will be the primary method for managing umbralisib related toxicities. Ublituximab and umbralisib therapy should be held upon onset of any of the following toxicities until recovery as outlined in Table 3 below. Upon recovery of toxicities as outlined in Table 3 below, umbralisib dosing should be the initial drug restarted. Ublituximab infusions should restart at least 7 days after umbralisib dosing has resumed and there has been no recurrence of the toxicity. One exception to this rule, are any toxicities related to infusion reactions. Upon recovery of any Grade 3 or greater infusion related toxicities back to baseline of less than or equal to Grade 1, the requirement of 7 days of umbralisib dosing before ublituximab dosing can be waived in order to keep patients on schedule during the first cycle induction. During the first cycle, if there is a toxicity observed that requires holding of therapy that would cause the dosing of ublituximab to fall out of window or schedule, then that dose should be skipped, the patient should reinitiate umbralisib upon recovery and be dosed with ublituximab at the next scheduled infusion per protocol. If there is a recurrence of toxicity felt attributable to ublituximab then further ublituximab infusions may be stopped at investigator discretion.

Table 3. Hematologic Grading Scheme for subjects entering with abnormal platelets or hemoglobin.

Hematologic Grading Scheme	
Grade	Decrease in platelets¹ or hemoglobin² from pretreatment value
0	0-10%
1	10.01-24%
2	24.01-49%
3	49.01-74%
4	≥74.01%

1. Platelet counts must be below normal levels for Grades 1 to 4. If, at any level of decrease, the platelet count is < 20 x 10⁹/L (20,000/µL), this will be considered Grade 4 toxicity.

2. Hemoglobin levels must be below normal levels for Grades 1 to 4. Baseline and subsequent hemoglobin determinations must be performed before any given transfusions. The use of erythropoietin will not affect grading of toxicity and use should be documented

Table 4. Dose delay and modification schema for umbralisib and ublituximab.

NCI-CTCAE Grade	Dose Delay and/or Modification
Hematologic Adverse Event	
Neutropenia	
Grade ≤ 2 neutropenia	Maintain current dose and schedule of umbralisib and ublituximab (if applicable). Consider supportive care as warranted.

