9.1.4 Stable Disease

Any subject who has not achieved a CR or a PR and do not demonstrate progressive disease, will be considered to have stable disease.

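### The primary ORR has no stated denominator, and the two response-evaluability rules differ; read as the analysis set, Section 11.4.2 would leave out early failures

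*Combined protocol and SAP*

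**What the plan says.** Sections 1.1, 9.1 and 11.2.1 name the endpoint, the response criteria and the interval method. None names the set of patients over which the ORR is computed. The passages that bear on it are these:

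- **Section 11.4.2**, under the heading Reporting and Exclusions: subjects will be "assessed for response to treatment if they have completed at least one cycle of ublituximab and umbralisib combination therapy".
- **Protocol Summary, Drug Administration and Study Schedule**, which sets its own condition for evaluating a subject's response: "if they complete two cycles of therapy or are noted to have documented clinical progression of disease prior to first study mandated radiographic assessments".
- **Section 11.4.1**, on toxicity: "All patients will be evaluable for toxicity from the time of their first treatment with ublituximab or umbralisib".
- **Section 11.2.1**, the planned precision: "With 12 patients enrolled in cohort A, an exact binomial (Clopper-Pearson) 95% confidence interval for the overall response rate", with a parallel sentence for cohort B.
- **Section 9.1.4**: "Any subject who has not achieved a CR or a PR and do not demonstrate progressive disease, will be considered to have stable disease".

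Ublituximab can also end early without a statement that umbralisib must end. Section 5.2.2 says "For any Grade 4 infusion related reaction, ublituximab should be stopped indefinitely". Section 6.2 says "If there is a recurrence of toxicity felt attributable to ublituximab then further ublituximab infusions may be stopped at investigator discretion".

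**The concern.** The plan has an explicit all-treated rule for toxicity and a conditional rule for response, side by side under a heading about exclusions. A reader could fairly take 11.4.2 to define the response-evaluable set. Two groups would then be missing from the primary ORR:

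1. Subjects who progress, die or stop all therapy before the end of Cycle 1. They are non-responders or, at best, have no documented response, so leaving them out raises the ORR.
2. Subjects who stop only ublituximab during Cycle 1, stay on umbralisib and later respond. Leaving out such a responder lowers the ORR.

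The analysis is descriptive and has no response threshold, so the estimate and its interval are the result. With two differing rules and no stated denominator, the analysis set could be settled after the data are seen. PFS and OS run from the first treatment day (Sections 9.3 and 9.4) and would still show the early failures, but both are exploratory.

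**Working it through.** **Timing.** Cycles are 28 days and Cycle -1 is umbralisib alone (Section 5.2). One completed combination cycle is reached at 28 + 28 = 56 days. The two cycles in the synopsis are 56 days if the lead-in counts, or 28 + 2 × 28 = 84 days if only combination cycles count. The cycle counts may therefore coincide; the early-progression clause is the firm difference.

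**Who each rule covers**, for events before the end of Cycle 1:

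| Subject | 11.4.2 | Synopsis |
|---|---|---|
| Documented clinical progression | No | Yes |
| Death without documented progression | No | No |
| Stops all therapy for toxicity, or withdraws | No | No |
| Stops ublituximab only, continues umbralisib | No, if the combination cycle counts as not completed | Yes after two cycles, if umbralisib alone counts as therapy |

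**The plan's own intervals.** The Clopper-Pearson 95% limits are Beta(0.025; x, n − x + 1) and Beta(0.975; x + 1, n − x). The inputs from Section 11.2.1 are n = 12 and rates of 55% and 40%.

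- Cohort A: x = 0.55 × 12 = 6.6 gives 24.96% to 82.54%, width 57.58. The plan states 25.0% to 82.5%, width 57.6.
- Cohort B: x = 0.40 × 12 = 4.8 gives 14.06% to 70.94%, width 56.88. The plan states 14.1% to 70.9%, width 56.9.

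Both reproduce, using all 12 enrolled as n and fractional responder counts.

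**Effect of the denominator.** The number of exclusions is an assumption. The planned 6.6 responders in cohort A lies between 6 and 7, so both are shown; 4.8 in cohort B is taken as 5.

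| Excluded | A, 6 responders | A, 7 responders | B, 5 responders |
|---|---|---|---|
| None | 6/12 = 50.0% (21.1–78.9) | 7/12 = 58.3% (27.7–84.8) | 5/12 = 41.7% (15.2–72.3) |
| 1 non-responder | 6/11 = 54.5% (23.4–83.3) | 7/11 = 63.6% (30.8–89.1) | 5/11 = 45.5% (16.7–76.6) |
| 2 non-responders | 6/10 = 60.0% (26.2–87.8) | 7/10 = 70.0% (34.8–93.3) | 5/10 = 50.0% (18.7–81.3) |
| 1 responder | 5/11 = 45.5% (16.7–76.6) | 6/11 = 54.5% (23.4–83.3) | 4/11 = 36.4% (10.9–69.2) |

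Leaving out one of each from 6/12 gives 5/10 = 50.0% (18.7–81.3), no shift in the estimate.

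**In expectation.** If a share d of subjects is excluded and all are non-responders, a true ORR of p is reported as p/(1 − d). With d = 1/12, 55% becomes 60% and 40% becomes 43.6%. With d = 2/12, they become 66% and 48%.

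**The case against.** Section 11.4.2 says who is assessed, not who is counted. It can be read as scheduling: Section 5.1.2.6 puts the first on-treatment CT before C2D1, the end of one combination cycle. The only n attached to the ORR is all 12 enrolled per cohort, which suggests that no exclusion was meant. Section 9.1.4 could be said to sweep in anyone without CR, PR or progression. The synopsis recovers early progressors.

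The second group may be rare. Section 2.4.5 reports Grade 3 or higher infusion reactions in 1% of subjects on the doublet; at that rate the chance of at least one among 12 is 1 − 0.99^12 = 11.4%, and the mandatory stop in 5.2.2 needs Grade 4. Section 6.2 lets a Cycle 1 ublituximab dose be skipped, and a completed cycle is not defined, so such a subject might still qualify. A subject who stops during the lead-in never receives the combination, so an all-treated set is not the only defensible one.

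Much of this stands. Exclusion is one reading, not a stated rule; the second group is probably small; and the shift is modest in a descriptive pilot. But the 12 enrolled figure is a planning calculation on fractional counts, and 9.1.4 is a response category that does not expressly cover subjects never assessed. The synopsis clause is absent from 11.4.2 and does not reach early death, toxicity or withdrawal. None of these passages supplies the denominator.

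**Conclusion.** The concern holds. The denominator of the sole primary endpoint is undefined, and the two evaluability rules differ at least on early progression. If 11.4.2 is applied as the response set, the expected net bias is upward, because early progression and death are non-responses. It is not upward in every case, since a responder who stopped only ublituximab could also be lost.

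In the examples one exclusion moves the estimate by 3.8 to 5.3 points, and two excluded non-responders move it by 8.3 to 11.7 points, against an interval about 57 points wide. These sizes rest on assumed exclusion counts, because the documents give no early-exit rate for this regimen. The point should be fixed before analysis, chiefly so that the choice of set cannot depend on the results.

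**What to change.** In Section 11.4.2 and the synopsis:

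- Define the primary ORR, per cohort, over all subjects who receive at least one dose of either study drug. This is the starting point already used in 11.4.1 and matches the time origin of PFS and OS.
- Count every subject without a documented response, including those never assessed, as a non-responder.
- Count any documented response, even if ublituximab was stopped early.
- State one evaluability rule, with a completed cycle defined, and use it in both places. Report the evaluable-only ORR under that rule as a labelled sensitivity analysis, shown as x/n.

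A separate conflict bears on when a subject becomes assessable: the synopsis places the first on-treatment scan before C3 and Section 5.1.2.6 before C2D1. Those passages must be reconciled.

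The cost is protocol and SAP wording, with no added patients or procedures. Section 5.5 already provides that "Subjects who discontinue study treatment for reasons other than disease progression or withdrawal of consent will be followed for progression free survival". Its CT schedule there is every 12 months or as clinically warranted, so it does not guarantee a response scan after an early stop; the non-responder rule covers that case. The downside is that the reported ORR may be slightly lower than an evaluable-only figure.
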